4.0 Background and Drug Information

4.1 Background

Telotristat etiprate is the United States Adopted Name (USAN) for the hippurate salt of telotristat ethyl, the ethyl ester prodrug of LP-778902. In vivo, telotristat etiprate dissociates to form telotristat ethyl which is rapidly converted through the activity of carboxylesterase 1 and 2 to its active metabolite LP-778902. Telotristat ethyl (XERMELO) is a novel, oral, small-molecule tryptophan hydroxylase (TPH) inhibitor that has a high molecular weight and acidic moieties, which inhibits it from crossing the blood-brain barrier. Telotristat ethyl has been shown to lower serotonin (5-HT) levels in the system by inhibiting TPH. Through inhibition of TPH, Telotristat ethyl reduces the production of peripheral 5-HT and the frequency of CS diarrhea and has been FDA approved for the treatment of carcinoid syndrome diarrhea. Two studies in patients with carcinoid syndrome suggested that telotristat etiprate, the hippurate salt of telotristat ethyl, reduced bowel movement (BM) frequency and decreased urinary 5-HIAA without overt CNS adverse effects (27,28). Although the name “telotristat etiprate” was previously granted by the United States Adopted Names Council and has been used in the literature, recent guidance from the US Food and Drug Administration recommends using the name of the neutral form (telotristat ethyl) rather than the name of the salt for drug products.

4.2 Preclinical Pharmacology Studies

Please refer to TerSera Therapeutics investigative brochure (IB) for details. Information in this proposal was derived from IB.

4.3 Preclinical Toxicology Studies

Please refer to TerSera Therapeutics investigative brochure (IB) for details.

4.4 Clinical Studies of telotristat ethyl in Humans

Please refer to TerSera Therapeutics investigative brochure (IB) for details

4.5 Rationale for telotristat ethyl (XERMELO) in patients with Carcinoid

Telotristat ethyl is indicated for the treatment of diarrhea in combination with SSA therapy in adults with inadequately controlled diarrhea on SSA therapy. This is thought to occur through the mediation of 5-HT. 5-HT is also implicated in the development of many of the signs and symptoms of carcinoid syndrome and carcinoid heart disease. A treatment which could further reduce 5-HT production may prove to be of immense clinical benefit. By adding a TPH inhibitor that can lower serotonin levels, telotristat ethyl could be of clinical benefit. One way to assess the potential of this clinical benefit is to look at the effect of telotristat ethyl on biomarkers such as NT-proBNP which have been associated with worsening cardiac prognosis. Furthermore, echocardiographic parameters and functional capacity changes can be clinically assessed.

4.6 Drug Product

4.6.1 Identity

Telotristat ethyl 250 mg and 500-mg tablets are white to off-white, coated, and oval. Placebo pills will be identical in size, shape, and color.

4.6.2 Drug Product Supply

Tablets will be supplied by TerSera Therapeutics and will include
TELOTRISTAT ETHYL 250 mg tablets.

PLACEBO MATCHING 250 mg tablets.

4.6.3 Storage

Telotristat ethyl should be stored at 25°C (77°F); excursions are permitted 15°C to 30°C (59°F to 86°F).

5.0 Patient Eligibility

5.1 Inclusions

- 5.1.1** Patients who are ≥ 18 years old will be eligible for the study.
- 5.1.2** Histopathologically-confirmed, metastatic neuroendocrine tumor and/or locally/regionally advanced neuroendocrine tumor
- 5.1.3** Documented history of carcinoid syndrome based on clinical parameters
- 5.1.4** Currently receiving stable-dose somatostatin analog (SSA) therapy defined as ≥ 2 months
 - 5.1.4.1** dose of long-acting release (LAR) or depot SSA therapy and on at least:
 - 5.1.4.1.1** Octreotide LAR at 30 mg every 4 weeks
 - 5.1.4.1.2** Lanreotide Depot at 120 mg every 4 weeks
 - 5.1.4.1.3** Patients who cannot tolerate SSA therapy at a level indicated above will be allowed to enter at their highest tolerated dose
- 5.1.5** Ability and willingness to provide written informed consent
- 5.1.6** Patients of childbearing potential must agree to use an adequate method of contraception during the study and for 30 days after the last dose of telotristat ethyl.
 - 5.1.6.1 a.** Childbearing potential is defined as those who have not undergone surgical sterilization (eg. documented hysterectomy, tubal ligation, or bilateral salpingo-oophorectomy) or those who are not considered postmenopausal (defined as 12 months of spontaneous amenorrhea).
 - 5.1.6.2 b.** Adequate methods of contraception, defined as having a failure rate of $<1\%$ per year, for patients or their partner include the following: condom with spermicidal gel, diaphragm with spermicidal gel, intrauterine device, surgical sterilization, vasectomy, oral contraceptive pill, depo-progesterone injections, progesterone implant (ie, Implanon®), patch (Ortho Evra®), NuvaRing®, and abstinence. If a patient is not sexually active but becomes active, he or his partner should use medically accepted forms of contraception.
- 5.1.7** ECOG 0-2

5.2 Exclusions

- 5.2.1** Prior telotristat exposure in the last 3 months
- 5.2.2** History of active treatment for malignancy, other than neuroendocrine tumor (malignancies that in the opinion of the Investigator are considered cured, may participate)
- 5.2.3** Treatment with any tumor directed therapy, including interferon, chemotherapy, mechanistic target of rapamycin (mTOR) inhibitors <4 weeks prior to screening, or hepatic embolization, radiotherapy, peptide receptor radionuclide therapy, and/or tumor debulking <12 weeks prior to screening
- 5.2.4** History of short bowel syndrome or other known causes of diarrhea unrelated to carcinoid syndrome
- 5.2.5** Clinically significant (as per primary investigators judgement) cardiac arrhythmia, bradycardia, tachycardia that would compromise patient safety or the outcome of the study
- 5.2.6** estimated glomerular filtration rate eGFR < 30ml/min
- 5.2.7** Hepatic laboratory values of aspartate transaminase (AST) or alanine aminotransferase (ALT):
 - 5.2.7.1** a. >5 x upper limit of normal (ULN) if patient has documented history of hepatic metastases; or
 - 5.2.7.2** b. >2.5 x ULN if no liver metastases are present
- 5.2.8** Pregnant or lactating patients
- 5.2.9** Patients receiving everolimus due to poor response to SSA
- 5.2.10** Life expectancy < 6 months
- 5.2.11** Any other clinically significant laboratory abnormality that would compromise patient safety or the outcome of the study as per primary investigators judgement
- 5.2.12** Any clinically significant and/or uncontrolled cardiac-related abnormality that would compromise patient safety or the outcome of the study including as per primary investigators judgement, but not limited to:
 - 5.2.12.1** Arrhythmia causing hemodynamic compromise
 - 5.2.12.2** Symptomatic severe valvular disease
 - 5.2.12.3** Symptomatic congestive heart failure classified by New York Heart Association (NYHA) Class IV

- 5.2.12.4** Evidence of ischemia on ECG with chest pain
- 5.2.12.5** Unstable angina pectoris
- 5.2.13** Current complaints of persistent constipation or history of chronic constipation, bowel obstruction or fecaloma within the past 6 months
- 5.2.14** Investigator assessment of known history and/or uncontrolled hepatitis B surface antigen (HBsAg), hepatitis C antibody (HCV Ab), or human immunodeficiency virus (HIV)-1 or HIV-2
- 5.2.15** History of substance or alcohol abuse (Diagnostic and Statistical Manual of Mental Disorders 5th edition [DSM-V] Criteria for Substance-Related Disorders) within the past 2 years
- 5.2.16** History of galactose intolerance, deficiency of Lapp lactase, or glucose-galactose malabsorption
- 5.2.17** Receipt of any investigational agent or study treatment (other treatment not approved by FDA for carcinoid syndrome or carcinoid heart disease) within the past 30 days
- 5.2.18** Existence of any surgical or medical condition that, in the judgment of the Investigator, might compromise patient safety or the outcome of the study
- 5.2.19** Presence of any clinically significant findings (relative to the patient population) during review of medical history or upon PE that, in the Investigator's opinion, would compromise patient safety or the outcome of the study (eg, psychiatric illness/social situations that would limit compliance with study requirements)
- 5.2.20** Unable or unwilling to communicate or cooperate with the Investigator for any reason

6.0 Treatment Plan

6.1 General

All patients should be registered with the Data Management Office Prometheus system.

6.2 Treatment Plan

Patients who present to the MD Anderson Cancer Center and have a confirmed diagnosis of carcinoid syndrome and/or carcinoid heart disease based on clinical, imaging, and/or expert physician diagnosis would be eligible for enrollment in the trial (see above for eligibility criteria). Patients will be referred directly from oncology clinic and/or by electronic medical record screening by the research team to determine eligibility. Patients would then be enrolled into one of 2 arms of the clinical trial in a stratified randomized, double-blinded fashion into a treatment arm (XERMELO + SSA) versus a placebo standard treatment arm (PLACEBO + SSA). A maximum of 79 participants will be recruited to participate in the study for 6 months.

6.2.1 Screening Criteria and Randomization plan

Written, Electronic, or Virtual informed consent will be obtained from all patients before beginning any study related screening procedures. The collection of adverse events will begin after patient has received his first dose of treatment. Participants will be allocated to one of two treatment arms by stratified block randomization method, considering age group (≤ 60 years vs. > 60 years) and disease status (with vs. without Carcinoid heart disease) as stratifying factors using Clinical trial conduct website (<https://biostatistics.mdanderson.org/ClinicalTrialConduct>).

6.2.2 Study Overview

Study Type: Prospective Clinical Trial

Enrollment: 79 participants

Allocation: Randomized 1: 1

Intervention Model Description: Participants were randomized to one of two treatment arms by stratified randomization method. Those who were randomized to treatment arm would

receive telotristat ethyl 500 mg po TID + SSA and those who were randomized to placebo arm would receive placebo + SSA

Blinding: Double (Participant and Investigators)

Primary Purpose: Treatment and disease progression

6.2.3 Treatment Arms

Treatment Arm: A

Experimental: 500 mg Telotristat Ethyl (2 tablets of 250 mg) TID with meals + SSA Patients who are currently on stable-dose somatostatin analog (SSA)

therapy (octreotide or lanreotide for 2 months) are randomized to receive one 500 mg telotristat ethyl tablet administered three times daily for 6 months in the treatment period.

Placebo/Standard Treatment Arm: B

Placebo: Placebo-matching telotristat ethyl tablet TID with meals + SSA Patients who are currently on stable-dose somatostatin analog (SSA) therapy (octreotide or lanreotide for 2 months) are randomized to receive one placebo-matching 500 mg telotristat ethyl tablet administered three times daily for 6 months in the treatment period

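### Section 6.2.3 gives two tablet counts for the same 500 mg TID dose, gives placebo only the single-tablet count, and does not fit the supply list in section 4.6.2

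*Combined protocol and SAP*

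**What the plan says.** Five places in the combined protocol and SAP bear on what a patient physically takes.

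- Section 6.2.3, Arm A heading line: "Experimental: 500 mg Telotristat Ethyl (2 tablets of 250 mg) TID with meals + SSA", that is, two tablets per dose.
- Section 6.2.3, Arm A narrative: patients are "randomized to receive one 500 mg telotristat ethyl tablet administered three times daily for 6 months in the treatment period", that is, one tablet per dose.
- Section 6.2.3, Arm B: the heading line reads "Placebo: Placebo-matching telotristat ethyl tablet TID with meals + SSA", with the tablet in the singular and no count. The narrative has patients "randomized to receive one placebo-matching 500 mg telotristat ethyl tablet administered three times daily for 6 months". Nowhere is placebo given as two tablets per dose.
- Section 4.6.1: "Telotristat ethyl 250 mg and 500-mg tablets are white to off-white, coated, and oval". It adds that placebo looks the same as active.
- Section 4.6.2: the listed supply is 250 mg active tablets and "PLACEBO MATCHING 250 mg tablets". No 500 mg tablet, active or placebo, is on the list.

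Sections 6.2.2 and 11.3 give the dose as 500 mg three times daily without a tablet count. Section 6.2.2 also specifies double blinding of participants and investigators.

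**The concern.** Section 6.2.3 is the operative dosing instruction, and it can be followed in more than one way. Two things depend on how it is read.

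The first is the dose delivered. The count in the Arm A narrative, applied to the only strength on the supply list, delivers less than the dose the trial sets out to test.

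The second is the blind. Only the active arm is ever described as taking two tablets. Matching appearance does not hide a difference in number, and under section 6.4 site staff count returned tablets at each visit. If the counts differed by arm, allocation could become apparent to people involved in the assessments that are open to judgement, such as causality grading, the walk test and the symptom questionnaire.

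Two related steps inherit the ambiguity. Section 6.3.2 sets a reduced level of 250 mg TID but gives no tablet count for either arm. Section 6.4 reconciles returned tablets against planned doses without saying how many tablets make one dose.

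**Working it through.** **Inputs.** Tablets per dose: 2 (6.2.3, Arm A heading) or 1 (6.2.3, Arm A narrative and Arm B). Strength: 250 mg (4.6.2; 6.2.3 Arm A heading) or 500 mg (4.6.1; 6.2.3 narratives). Doses per day: 3. Reduced level: 250 mg TID (6.3.2). Treatment length: 24 weeks = 168 days (8.14).

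**Formula.** Daily dose = tablets per dose × strength × 3. Daily tablets = tablets per dose × 3.

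**Step 1: the plan's own dose.**
- Arm A heading: 2 × 250 × 3 = 1500 mg/day.
- Arm A narrative: 1 × 500 × 3 = 1500 mg/day.

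Both reproduce 500 mg TID, so the two descriptions agree on dose.

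**Step 2: one tablet per dose with the listed supply.**
- 1 × 250 × 3 = 750 mg/day.
- 750 / 1500 = 0.5, half the stated dose.
- The reduced level in 6.3.2 is 250 × 3 = 750 mg/day, the same amount.

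**Step 3: tablet counts by arm.**

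| Text followed | Arm A tablets/day | Arm B tablets/day |
|---|---|---|
| Both narratives | 1 × 3 = 3 | 1 × 3 = 3 |
| Arm A heading, Arm B text | 2 × 3 = 6 | 1 × 3 = 3 |

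Over 168 days the second row is 6 × 168 = 1008 tablets against 3 × 168 = 504, a 2:1 difference.

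**Step 4: the reduced level.** If a full dose is two 250 mg tablets, the step down to 250 mg is from two tablets to one, and a placebo patient already on one tablet has no matching step. If a full dose is one 500 mg tablet, the step down needs a different tablet, and 4.6.2 lists no 500 mg active or matching placebo to step down from.

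**Step 5: exposure so far.** Section 11.1 reports 28 subjects who completed six months, 13 still in follow-up and 6 withdrawn after starting treatment: 28 + 13 + 6 = 47 had received study drug. A further 19 were planned, plus 3 not yet randomized. The wording therefore affects both past dispensing, which can be checked, and future dispensing.

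The sample size and power statements do not use any of these inputs and are unaffected.

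**The case against.** The strongest reply is that the plan never states a starting dose other than 500 mg TID. Sections 6.2.2, 6.2.3 and 11.3 agree, 6.3.2 treats 250 mg as one level lower, and 11.3 contrasts 250 mg with the dose used here. To reach 750 mg/day a reader must take the single-tablet count and disregard the strength in the same phrase. The two narratives in 6.2.3 are also symmetric, so the 6 versus 3 contrast arises only by pairing the Arm A heading with the Arm B text. No passage directs unequal counts. Dispensing was already under way, and pharmacy instructions may have settled the matter.

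That stands as a limit on the consequences. It does not remove the conflict: the two Arm A descriptions cannot both describe what is dispensed, and placebo has no count to match the heading.

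Three stronger readings are tempting and not supported:

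- A reader might infer that the plan states two different doses. It does not (step 1).
- A reader might infer that no 500 mg tablet is supplied at all. Section 4.6.2 lists what the supply includes, which does not strictly exclude other strengths, and 4.6.1 describes a 500 mg tablet. If one were supplied, the Arm A heading would still disagree with the sentence below it.
- A reader might infer that the 70% compliance endpoint would be mis-scored by a factor of two. Section 11.2 defines compliance as medication taken divided by medication provided. That ratio cannot exceed 100%, and it gives 100% to a patient who was provided with and took one tablet per dose. What remains unclear is only the number of tablets per planned dose in the 6.4 reconciliation.

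**Conclusion.** The point holds as an inconsistency in tablet count, strength and supply, not as a conflict in the stated dose. No passage reconciles sections 4.6.1, 4.6.2 and 6.2.3.

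The possible size is a halving of the active dose (750 against 1500 mg/day) if one tablet per dose is applied to the listed 250 mg supply, or a visible 6 versus 3 tablets a day if Arm A follows its heading and Arm B its text. Each result requires that particular reading. The documents do not show that any patient was under-dosed or that the blind was broken, and without the dispensing instructions neither can be confirmed or ruled out. Because the text governs both the treatment tested and the blind, it should be corrected and not left to interpretation.

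**What to change.** The sponsor should reconcile sections 4.6.1, 4.6.2 and both arm descriptions in 6.2.3 so that:

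- one tablet count and one strength per dose are stated, in the same words for active and placebo;
- that count and strength match the tablets actually supplied;
- section 6.3.2 carries the same matched-count wording for both arms at the reduced level;
- section 6.4 states how many tablets make one planned dose when returns are counted.

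Labels and dispensing instructions, including those already used, should be checked against the reconciled text. Which regimen is correct is for the sponsor to state; this review proposes none.

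The cost is a wording amendment and a label and pharmacy check. No new procedure, visit or analysis is needed.

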6.3 Dose of Modifications of telotristat ethyl

6.3.1 Definitions

6.3.1.1 Interruption: temporary stoppage of telotristat ethyl but then resuming the treatment(s) within 3 weeks

6.3.1.2 Discontinuation: premature withdrawal from telotristat ethyl defined as a dose interruption lasting for >3 weeks

6.3.2 Dose Adjustments for adverse events related to the study drug

Adverse Events will be graded as follows (NCI CTCAE version 5.0)

Grade 1 No change in dose
Grade 2 Hold until ≤Grade 1. Resume at same dose level.
Grade 3 Hold until ≤Grade 1. Resume at 1 dose level lower (250 mg tid).
Grade 4 Hold and contact the Primary Investigator

Dose can also be adjusted or discontinued per PI's discretion for patients' safety.

*Patients unable to tolerate 250 mg tid should be discontinued from telotristat ethyl. **Constipation and abdominal pain dose adjustment is different (see below)

6.3.3 Recommended management for the following AEs:**6.3.3.1** Nausea and/or vomiting: treatment with antiemetics**6.3.3.2** Diarrhea: treat underlying cause and/or with antidiarrheal**6.3.3.3** Gastrointestinal toxicity**6.3.3.3.1** Monitor concomitant medication usage**6.3.3.3.2** Constipation (Grade 1 and above): initiate treatment as clinically indicated; examples of therapies include: laxatives, enemas, suppositories, psyllium hydration, over-the-counter (OTC) agents**6.3.3.3.3** Abdominal pain (Grade 1 and above): initiate treatment as clinically indicated; examples of therapies) include: analgesics, anti-gas/bloating agents**6.3.3.3.4** Hold telotristat ethyl for Grade 2 constipation or abdominal pain until \leq Grade 1.**6.3.3.3.5** Discontinue telotristat ethyl for Grade 3 constipation or abdominal pain*(please note this is different than above table)**6.3.3.4** Suicidal ideation: discontinue telotristat ethyl**6.4 Treatment Compliance**

Patients will be asked to bring their unused or unopened bottles of telotristat ethyl to each visit. Patients will be allowed to ship their unused and/or unopened bottles of telotristat ethyl back to PI at MDAnderson if traveling is impossible/restricted. At each visit study site personnel will count returned tablets and reconcile the counts against planned number of doses for that interval. All dosages prescribed and dispensed to the patient, dose modification(s), and missed dose(s), including planned dose interruptions during the study must be recorded. Site personnel are to clarify any discrepancy and record this information.

Patients must maintain at least 70% compliance at clinical visits (3 month interval including allowed window; see section 8 for details) in dosing to be deemed as compliant.

6.5 Missed Doses

In the event of a missed or vomited telotristat ethyl dose, patients will take their subsequent dose at the next scheduled time point, following the tid dosing regimen of approximately every 6 hours. A dose outside of a 3-hour window for telotristat ethyl should be considered missed. Missed or vomited doses will not be made up.

6.6 Duration of Therapy

The total duration of therapy with the study drug telotristat ethyl will be 6 months as part of the clinical trial assessment.

6.7 Prohibited and Restricted Therapies During and Prior to the Study

Treatment with any tumor directed therapy, including interferon, chemotherapy, mechanistic target of rapamycin (mTOR) inhibitors <4 weeks prior to screening, or hepatic embolization, radiotherapy, radiolabeled SSA, and/or tumor debulking <12 weeks prior to screening. Patients receiving everolimus due to poor response to SSA

7.0 Baseline Evaluation

- 7.1 Obtain Informed Consent (telemedicine technology and language assistant may be used). We will follow the Office of Clinical Research Standard Operating Procedure (SOP) for informed consent process. During this process, the iConsent feature within EPIC will be utilized. The consent process can be completed either in-person or remote.
- 7.2 Complete history and physical examination including vital signs, NYHA classification, and ECOG (telemedicine technology and language assistant may be used)
- 7.3 CBC with differential, Liver panel (to include AST, ALT, bilirubin, albumin), basic metabolic panel (Sodium, potassium, bicarbonate, chloride, BUN, creatinine, glucose) within 6 weeks (**-asterisk- labs and tests maybe done 3 weeks prior or up to 3 weeks after clinical baseline/follow-up date)
- 7.4 ECG within 6 weeks**
- 7.5 Serum Pregnancy test for females of childbearing age within 1 week
- 7.6 MD Anderson Symptom Inventory MDASI module (in Appendix) within 6 weeks (telemedicine technology and language assistant may be used)**
- 7.7 Echocardiography with a 2D transthoracic echocardiography (2D TTE), 3-dimensional echocardiography (3D TTE), and myocardial strain of the left and right ventricle within 6 weeks**
- 7.8 Plasma 5-HIAA collection within 6 weeks** (it will be kept frozen in Cryogene lab and will be transferred to Frontage Lab for analysis. More information is included in the lab manual.)
- 7.9 Cardiac biomarkers to include: N-terminal pro B-type natriuretic peptide (NT-proBNP) and high sensitivity troponin T (HS-troponin T) within 6 weeks**
- 7.10 6 minute walk test (6MWT) (in Appendix) where distance is recorded in meters within 6 weeks**

